8.3 Reporting

8.3.1 UADEs

UADEs must be reported by the clinical investigator to the sponsor and the reviewing IRB, as described below:

For this device study, investigators are required to submit a report of a UADE to the FDA, the manufacturer of the device and the UNC IRB as soon as possible, but in no event later than 10 working days after the investigator first learns of the event (§ 812.150(a)(1)), using the MedWatch Form 3500A. Sponsors (LCCC) must immediately conduct an evaluation of a UADE and must report the results of the evaluation to FDA, the UNC IRB, and participating investigators within 10 working days after the sponsor first receives notice of the effect (§§ 812.46(b), 812.150(b)(1)).

For this device study, we will submit a report of a UADE to the manufacturer and the IRB as soon as possible, but no later than 10 working days after the investigators first learn of the event.

8.3.2 UP

Any events that meet the criteria for "Unanticipated Problems" as defined by UNC's IRB must be reported by the Study Coordinator using the IRB's web-based reporting system.

Any unanticipated problem that occurs during the conduct of this study and that meets **at least** the first two criteria listed in section 8.2 must be reported to the UNC IRB using the IRB's web-based reporting system.

9.0 Data and Safety Monitoring Plan

The Principal Investigator will provide continuous monitoring of patient safety in this trial with periodic reporting to the Data and Safety Monitoring Committee (DSMC).

Meetings/teleconferences will be held at a frequency dependent on study accrual, and in consultation with the study Biostatistician. These meetings will include the investigators as well as protocol nurses, clinical research associates, regulatory associates, data managers, biostatisticians, and any other relevant personnel the principal investigators may deem appropriate. At these meetings, the research team will discuss all issues relevant to study progress, including enrollment, safety, regulatory, data collection, etc.

The team will produce summaries or minutes of these meetings. These summaries will be available for inspection when requested by any of the regulatory bodies charged with the safety of human subjects and the integrity of data including, but not limited to, the oversight (Office of Human Research Ethics (OHRE) Biomedical IRB, the Oncology Protocol Review Committee (PRC) or the North Carolina TraCS Institute Data and Safety Monitoring Board (DSMB).

The UNC LCCC Data and Safety Monitoring Committee (DSMC) will review the study on a regular (quarterly to annually) basis, with the frequency of review based on risk and complexity as determined by the UNC Protocol Review Committee. The UNC PI will be responsible for submitting the following information for review: 1) safety and accrual data including the number of patients treated; 2) significant developments reported in the literature that may affect the safety of participants or the ethics of the study; 3) preliminary response data; and 4) summaries of team meetings that have occurred since the last report. Findings of the DSMC review will be disseminated by memo to the UNC PI, PRC, and the UNC IRB and DSMB.

10.0 STATISTICAL CONSIDERATIONS

This is a nonrandomized, single-center study. The primary purpose and endpoint of this study is to compare, in a radiologist reader study, the sensitivity and specificity of the acoustic angiography system to the b-mode ultrasound with pathology as the reference standard.

10.1 Sample Size and Accrual

10.1.1 Primary analysis

For power calculation, the null hypothesis is that the specificity of acoustic angiography system is the same as the standard of care (b-mode ultrasound), which is assumed to be 70%. (We will determine the specificity of b-mode ultrasound during the trial to confirm that the 70%

represents the specificity in the hands of UNC radiologists) Under the alternative, we expect that the specificity of the new device is at least 90%. The specificities are measured relative to pathological diagnosis as the reference standard. With 60 lesions and 5 readers, where we anticipate that roughly half will be malignant, assuming the correlation from the same patient to be 0.5 and the readers to read different patients independently, the power to see specificity at least larger than 90% is 88% (the variance of the estimated specificity is calculated to be less than $0.6^2 \cdot 0.25/30$) at the significance level 0.05 using one-side test. Although we will study both sensitivity and specificity, our power calculation is based on specificity.

10.1.2 Secondary Analysis

Sixty (60) women scheduled to undergo breast biopsy based on an abnormal ultrasound finding will be enrolled. We assume the AUC for the b-mode ultrasound images is 60% with range 60%~80%, and AUC difference of 10%. Assuming that the prevalence of noncancerous lesions in the sample population will be approximately 50%, the study will be powered at least at 80% with 56 patients and 5 readers.

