1.2 Traditional Breast Cancer Screening and Diagnosis

Breast cancer is the most common cancer type among women. Approximately 10% of women in the United States develop breast cancer during their lifetime and 30% to 40% of these patients will die from it.[33, 34] Mammography is an effective tool for the early detection of breast cancer in the majority of women.[35] However, for women with dense breast tissue (considered an independent risk factor for breast cancer) and younger women, mammography performs poorly due to lower sensitivity and specificity in these groups.[37] For young women with heritable mutations who wish to begin screening at a younger age, these limitations are especially problematic.[38] Additionally, mammography is less sensitive in women who have undergone breast augmentation. Given these limitations, most of these women may undergo additional imaging with breast ultrasound or Magnetic Resonance Imaging (MRI).

MRI is time consuming, extraordinarily costly, and has limited availability, especially among rural and underserved populations. Another screening option, breast ultrasound (without contrast), is widely used when additional imaging beyond mammogram is required due to its real-time imaging capability (>30 images per second), portability, safety (does not involve radiation), and relatively low cost compared to breast MRI. Unfortunately, while breast ultrasound is highly sensitive (96%), it is less specific (70%),

resulting in a high false positive rate. This results in unnecessary biopsies with associated complications, additional follow-up and negative psychosocial impacts on patients, e.g., significant anxiety. A significant clinical need exists to improve breast ultrasound sensitivity and specificity.

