1.5 Rationale

One main limitation to the widespread use of contrast enhanced ultrasound clinically has been the lack of availability of state-of-the art contrast imaging approaches available to clinicians. However, contrast ultrasound will likely become far more widespread as new imaging techniques, such as acoustic angiography, demonstrate their usefulness and become available on commercial ultrasound systems. We propose to evaluate a novel ultrasound method that could potentially improve the sensitivity and specificity of traditional breast ultrasound. Increasing the accuracy of diagnostic imaging in high risk patients could provide substantial clinical benefit by improving diagnosis, preventing over-treatment, and reducing healthcare costs.

LCCC1748 is designed to compare the sensitivity and specificity of contrast enhanced ultrasound (acoustic angiography) to the sensitivity and specificity of conventional ultrasound in women scheduled to undergo a biopsy based on pre-study imaging results. The gold standard for sensitivity and specificity, then, will be based on pathological results. The Breast Imaging Reporting and Data System (BIRADS) is used by radiologists who read mammograms, ultrasounds and MRIs to indicate their level of suspicion of the possibility of breast cancer. Scores range from 0 to 6, with scores of 4-5 indicating suspicious results, while 6 indicates an existing diagnosis of breast cancer. This study is limited to women with a score of 4-5 based on pre-study imaging.

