3.0 ELIGIBILITY

3.1 Inclusion Criteria

Subject must meet all of the inclusion criteria to participate in this study:

- 3.1.1 Women \geq 18 years old
- 3.1.2 Patient had a diagnostic breast ultrasound study performed at UNC
- 3.1.3 Scheduled for a core needle or surgical breast biopsy of at least one breast lesion that is 2 cm or less in size and 3 cm in depth from the skin surface
- 3.1.4 Lesion visualized on ultrasound
- 3.1.5 Able to provide informed consent
- 3.1.6 Negative urine pregnancy test in women of child-bearing potential

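### The 70% b-mode specificity cannot be confirmed in women already selected by suspicious imaging, and that selection can favour the new device on specificity

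*Combined protocol and SAP*

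**What the plan says.** Section 1.2 gives the general performance of breast ultrasound: "while breast ultrasound is highly sensitive (96%), it is less specific (70"%). It links the false positives to biopsy: "This results in unnecessary biopsies with associated complications".

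Section 10.1.1 uses the same specificity for b-mode in the power calculation, "which is assumed to be 70"%, against 90% for acoustic angiography. It adds: "We will determine the specificity of b-mode ultrasound during the trial to confirm that the 70"% figure holds for UNC radiologists.

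The sample is described in three places:
- Section 10.1.2: women "scheduled to undergo breast biopsy based on an abnormal ultrasound finding".
- Section 1.5: "This study is limited to women with a score of 4-5 based on pre-study imaging".
- Section 3.1: "Patient had a diagnostic breast ultrasound study performed at UNC" and "Lesion visualized on ultrasound". A suspicious ultrasound result is not itself listed as a criterion.

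Section 10.2.1 estimates sensitivity and specificity for both modalities in this sample and gives confidence intervals for the differences. Scores of +1 and +2 count as malignant; -2, -1 and 0 do not. No section discusses the effect of selecting lesions on a prior imaging read.

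**The concern.** A specificity of 70% for breast ultrasound in general use means that, of all benign lesions examined, 70% are read as negative. Those true negatives mostly do not go to biopsy, so few of them can enter this trial. The benign lesions that do enter are mainly ones that clinical imaging called suspicious. Where ultrasound was the trigger, the clinical ultrasound read has 0% specificity in the sample by construction. A second b-mode read of the same lesions will tend to repeat part of that error.

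Two things are at stake. The trial's b-mode specificity does not estimate the 70% on which the power statement rests, so it can neither confirm nor refute it. The paired specificity difference may also partly reflect how the lesions were chosen. A device no more specific than b-mode across all lesions could then be reported as more specific, on the one endpoint that was powered.

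**Working it through.** **1. The plan's own figure.** Inputs from section 10.1.1: 30 benign lesions, 5 readers, within-patient correlation 0.5, specificity 70% against 90%, one-sided 0.05.
- Reader factor: (1 + 4 × 0.5)/5 = 0.6.
- Variance: 0.6 × 0.25/30 = 0.005, so SE = 0.0707.
- Power: Φ(0.20/0.0707 − 1.645) = Φ(1.18) = 88.2%, which matches the stated 88%.

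The printed variance squares the 0.6 and would give 97.8%; that is a separate matter. What counts here is that the 88% is a one-sample calculation. The 70% is treated as known and carries no sampling error.

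**2. The same effect as a paired difference.** Suppose each modality's average has variance 0.005 and the two averages have correlation c, which the documents do not give. The variance of the difference is 2 × 0.005 × (1 − c).
- c = 0: SE = 0.100, power = Φ(2.00 − 1.645) = 64%.
- c = 0.5: SE = 0.0707, power = 88%.

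Power for the planned comparison is therefore below 88% if c is under 0.5 and above it if c is over 0.5, before any change in the b-mode value itself.

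**3. Effect of selection, simple model.** Suppose both modalities have specificity S = 0.70 and sensitivity Se = 0.96 before selection, and the enrolling read has the same values. Let r be the correlation between a study read and the enrolling read, both taken as yes/no results. The values of r are assumed.
- Benign: P(both positive) = (1 − S)² + rS(1 − S). Dividing by (1 − S) and subtracting from 1 gives specificity among enrolled lesions = S(1 − r).
- Malignant: in the same way, sensitivity among enrolled lesions = Se + r(1 − Se).

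| r, b-mode | r, acoustic angiography | Specificity, b-mode | Specificity, acoustic angiography | Specificity gap | Sensitivity gap |
|---|---|---|---|---|---|
| equal | equal | equal | equal | 0 | 0 |
| 0.3 | 0.1 | 49% | 63% | +14 points | −0.8 points |
| 0.5 | 0.2 | 35% | 56% | +21 points | −1.2 points |
| 0.7 | 0.3 | 21% | 49% | +28 points | −1.6 points |

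Gaps are acoustic angiography minus b-mode: 0.70 × (r for b-mode − r for acoustic angiography) for specificity, and −0.04 × the same difference for sensitivity.

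**4. Check with a second model.** This uses bivariate-normal latent scores with the same 96% and 70% before selection. Its correlations are on the latent scale, so they are not interchangeable with r above.
- 0.5 and 0.25: specificity 48% against 60% (+12 points); AUC 0.904 against 0.926.
- 0.7 and 0.25: specificity 36% against 60% (+23 points); sensitivity 97.4% against 96.3%; AUC 0.890 against 0.925.
- 0.5 and 0.5: no specificity difference.

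The paired one-sided 0.05 specificity test was simulated with 30 benign lesions, 5 readers, an assumed latent correlation of 0.7 between readers, and 2,000 trials per setting. When unselected specificity is equal, it rejects in about 5-7% of trials without selection. With selection it rejects in 37% (0.5 and 0.25) or 67% (0.7 and 0.35), and in 5-6% when the two correlations are equal.

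**5. Which b-mode images are read.** Section 11.4 puts the images that led to biopsy into the reader study. Section 4.3.2 describes conventional ultrasound just before acoustic angiography, for localization. Section 5.0 describes b-mode on the research scanner. Re-reading the biopsy-triggering images would push the b-mode correlation up; new images from a different probe could bring it down. The documents do not settle this.

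**The case against.** A reader might infer that the plan contains two tests, one against 70% and one against in-trial b-mode, which could give opposite answers. It does not. Section 10.1.1 brings in the 70% for power only, and section 10.2.1 already plans the within-trial difference.

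A reader might also infer that the whole primary comparison is tilted toward acoustic angiography. That is too broad: for sensitivity, selection slightly favours b-mode.

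Nor do the documents show that every benign lesion enrolled is a b-mode false positive, or that no ultrasound-negative cancer can enter. Only section 10.1.2 names ultrasound as the trigger. Sections 1.1, 1.5 and 4.1 speak of pre-study imaging, and section 3.1 asks only that ultrasound was done and the lesion was visible. A lesion referred on another modality would weaken the effect.

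Two further points have force. The readers' +1/+2 cut-off may be stricter than BI-RADS 4-5, which could offset some or all of the fall in b-mode specificity. And the sentence on confirmation can be read as a modest check of a planning value for UNC radiologists. Even so, the check would compare two different quantities.

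Finally, the biopsy-bound population is openly stated and may be the right one. No section makes an explicit claim about unselected women. Among referred lesions, the paired difference is a legitimate estimate for that group. The difficulty arises only if it is read as a general comparison with b-mode.

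**Conclusion.** The point holds in a limited form. From the text alone, with no assumed number, b-mode specificity in this sample is a different quantity from the general 70% and cannot confirm it. The 88% describes power against that fixed value, not power for the paired comparison in section 10.2.1.

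The tilt toward acoustic angiography on specificity and AUC is conditional. It needs b-mode re-reads to follow the enrolling read more closely than acoustic angiography reads do. That is plausible, since b-mode shares its modality with an ultrasound enrolling read while acoustic angiography adds contrast and microvascular signal, but it is not shown. The simple-model gap runs from 0 with equal correlations to 28 points at an assumed 0.7 and 0.3. The 21 points at 0.5 and 0.2 are close to the planned 20-point effect only because of the inputs chosen. The opposite effect on sensitivity is 1 to 2 points in these examples. The true size cannot be found from the documents.

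**What to change.** 1. In section 10.1.1, delete the sentence about confirming 70%. State that the 88% is a one-sample calculation against a fixed 70% taken from general use. Restate power for the paired difference already planned in section 10.2.1, over a range of b-mode specificities plausible in biopsy-referred lesions and a range of between-modality correlations, with the sample size unchanged.
2. In sections 2.3 and 10.2.1, state that estimates are conditional on referral to biopsy after a BI-RADS 4-5 read, and that this selection pushes specificity and sensitivity in opposite directions. State which b-mode images the readers score, and reconcile sections 4.3.2, 5.0 and 11.4.
3. Limit the conclusion to biopsy-referred lesions: benign biopsies that might be avoided and cancers that would be missed. Make no general claim of higher specificity than b-mode.

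Cost: protocol and SAP wording plus one power calculation, with no added patients or procedures. The downside is a narrower claim and a power figure that may be lower than 88%.

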10.2 Data Analysis Plans

10.2.1 Primary Analysis

This is a prospective study to assess the diagnostic performance of the newly developed device. The **primary outcome of interest is the sensitivity and specificity of the acoustic angiography device as compared to b-mode ultrasound**. The sensitivity and specificity can be estimated non-parametrically as the proportion of the lesions which are distinguished as malignant versus non-malignant compared to the reference. This estimate will be calculated for each reader then averaged over all the readers. The standard error of the average sensitivity and specificity estimate will be calculated using the bootstrap method, where each patient is treated as independent unit with 5 ratings. The confidence interval of the final estimate will be provided using the normality assumption.

Furthermore, we will estimate the sensitivity and specificity of the b-mode ultrasound in this study and compare it with the sensitivity and specificity estimate of the acoustic angiography device using the bootstrap approach and the confidence interval of their differences will be provided using the normality assumption.

Malignancy scores of +1 and +2 will be considered malignant. Scores of -2, -1, and 0 will be considered not malignant. The confidence of malignancy will be used independently

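### The normal-theory bootstrap interval for each modality's sensitivity and specificity under-covers as the true value nears 100%; the paired difference interval is much less affected

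*Combined protocol and SAP*

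**What the plan says.** Section 10.2.1 estimates sensitivity and specificity as proportions for each reader and averages them over the readers. The standard error comes from a bootstrap "where each patient is treated as independent unit with 5 ratings". For the averaged estimate, "The confidence interval of the final estimate will be provided using the normality assumption". B-mode is estimated in the same study, and for the comparison "the confidence interval of their differences will be provided using the normality assumption". The section gives no confidence level, transformation, rule at the boundary or small-sample correction.

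Section 10.1.1 supplies the operating point: "With 60 lesions and 5 readers, where we anticipate that roughly half will be malignant", and "assuming the correlation from the same patient to be 0.5". B-mode specificity is taken as 70%, and for acoustic angiography "we expect that the specificity of the new device is at least 90" per cent. No sensitivity is assumed for the device. Section 1.2 gives 96% as the sensitivity of breast ultrasound without contrast, as background.

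**The concern.** An interval of the form estimate ± z × SE works well when the estimate is roughly symmetric and its SE does not depend on where it falls. Neither is true for a proportion of 90% or more on about 30 independent lesions. The estimate is skewed, and its bootstrap SE shrinks as the estimate approaches 1. Trials that overestimate accuracy by chance therefore also report the narrowest intervals. If every reader is right on every lesion of a class, the SE is zero and the interval is 100% to 100%.

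At stake is the reported precision of each modality's accuracy. The design expects device specificity of 90% or more, which is where the method is weakest.

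**Working it through.** **Inputs.** From 10.1.1: 30 lesions per class (half of 60), 5 readers, correlation 0.5, device specificity 0.90, b-mode specificity 0.70. From 1.2: 0.96, as background only. From 10.2.1: patients resampled, readers not, normal-theory limits. Assumed: 95% level, the same accuracy for all readers, exactly 30 lesions per class unless noted.

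**Check that the inputs are read correctly.** The variance factor for 5 ratings with correlation 0.5 is (1 + 4 × 0.5)/5 = 0.6. Then SE² = 0.6 × 0.25/30 = 0.005 and SE = 0.0707. One-sided power against a fixed 70% is Φ(0.20/0.0707 − 1.645) = Φ(1.18) = 88.2%, which matches the stated 88%. The variance as printed, with 0.6 squared, would give 97.8%. The exponent may be an artefact of PDF reading, and 0.6 is used below.

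**By hand.** True SE = √(0.6 × p(1−p)/30).
- p = 0.90: SE = 0.0424, 1.96 × SE = 0.083, upper limit 0.983.
- p = 0.96: SE = 0.0277, 1.96 × SE = 0.054, upper limit 1.014.

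At 0.96, an interval centred exactly on the truth already runs past 100%.

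**Single-modality coverage.** 40,000 simulated trials per setting, beta-binomial ratings, ideal patient-level bootstrap SE:

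| True value | Coverage | Interval wholly above truth | Wholly below |
|---|---|---|---|
| 0.70 | 93.1% | 4.9% | 2.0% |
| 0.90 | 89.1% | 10.3% | 0.7% |
| 0.96 | 77.8% | 22.0% | 0.2% |

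Nominal is 2.5% on each side. At 0.96 the upper limit exceeds 100% in about 77% of trials, and the interval has zero width in about 6%.

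**Sensitivity to assumptions.**
- Four models for the within-patient correlation: 77-78% at 0.96 and 86-89% at 0.90 (the low value is an all-or-none model).
- Actual bootstrap, 1,000 resamples, 3,000 trials: 77.9% and 88.9%.
- Random number of lesions per class: 78.9% and 88.6%.
- Correlation from 0.2 to 0.7: 87% down to 73% at 0.96, and 91% down to 88% at 0.90.
- A percentile bootstrap is no cure: 80.7% at 0.96 and 90.7% at 0.90.

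**Paired difference.** Patient effects correlated 0, 0.5 and 0.8 between modalities:

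| True values | Coverage | Misses overstating the difference | Misses understating it |
|---|---|---|---|
| 0.90 vs 0.70 | 93.1-93.4% | 1.9-3.0% | 3.6-5.1% |
| 0.70 vs 0.70 | about 94% | symmetric, about 3% each side | |
| 0.90 vs 0.90 | about 94% | symmetric, about 3% each side | |
| 0.96 vs 0.96 | 96-97% | symmetric, about 2% each side | |
| 0.96 vs 0.90 | 89.7-92.7% | 0.8-1.5% | 5.8-9.6% |

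Exchanging the modalities in the last row mirrors it, so a true loss of the device against b-mode would be understated in the same way as a true gain.

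**Does the remedy work?** A Wilson interval with effective n = p(1−p)/SE², left unbounded, covers only 88.7% at 0.96 and 92.6% at 0.90, because the SE is itself unstable there. With effective n held between 30 and 30/0.6 = 50, coverage is 95.6-96.7% for true values of 0.70 to 0.96 at correlation 0.5. It is 94.3-96.1% at correlation 0.7 and about 99% at 0.2. Difference limits built from these intervals cover 94.7-98.6% in the settings tried. At 0.90 vs 0.96 they raise coverage from 90-92% to 97-98%, and misses that understate the difference drop from 6-10% to about 1-2%.

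**The case against.** The strongest reply is that the primary outcome in 10.2.1 is the device as compared with b-mode, so the difference interval matters most, and it is nearly sound at the only design pair, 0.90 vs 0.70. That stands. No decision rule is tied to the single-modality limits; they describe each modality.

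A second reply is that 96% is not a planning value for this analysis. That also stands. It sits poorly with 10.1.2, which puts b-mode AUC at 60% with a range up to 80%. Sensitivity 96% with specificity 70% implies, for a concave ROC curve, an AUC of at least (0.96 + 0.70)/2 = 0.83. With specificity 70% and AUC no higher than 80%, sensitivity is at most 2 × 0.80 − 0.70 = 90%. The 78% coverage therefore shows what happens near the boundary; it is not a forecast. The shortfall at the design value of 90% is about 6 points.

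A reader might infer that the error favours the device. In a one-sided test against a fixed 70%, which is how 10.1.1 frames power, this SE does give a type I error of 7.9% instead of 5%. But 10.2.1 estimates b-mode in the same patients and compares by the difference. There the errors are symmetric at equal values and lean slightly against the device at 0.90 vs 0.70. The single-modality error flatters b-mode just as readily.

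A third reply is that the bound of 50 builds in the plan's correlation of 0.5. It holds up at 0.7. At 0.2 it is conservative: at 0.90 the average width is 16.8 points against 12.3 for the normal interval.

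**Conclusion.** The point holds for the single-modality intervals. At the plan's own 90%, a nominal 95% interval misses about 11% of the time instead of 5%, with the lower limit too high in about 10% of trials against 2.5% nominal. The problem worsens towards 100% and is small at 70%. It overstates accuracy for whichever modality is near 100%. The documents do not support a claim that it specifically favours the device, or that the primary comparison is badly wrong. The difference interval is close to nominal except when both accuracies are high and unequal, where coverage is 90-93% and the true difference is mostly understated.

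These figures rest on an assumed 95% level, about 30 lesions per class, correlation 0.5 and common accuracy across readers. The direction does not change across the correlation models and values tried. It is worth correcting before analysis because the remedy is cheap.

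**What to change.** In 10.2.1:

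1. State the confidence level.
2. For each modality's sensitivity and specificity, use a Wilson interval with effective n = p(1−p)/SE_boot². Bound it below by the observed number of lesions in that class (n) and above by n/0.6, and use the upper bound when SE_boot is zero. With 30 lesions and every rating correct, the lower limit is then 50/(50 + 1.96²) = 92.9% instead of 100%.
3. For the difference, use MOVER limits from these intervals. With d = p₁ − p₂, limits (l, u) for each modality and r the estimated correlation between the two averaged estimates:
   - lower = d − √[(p₁−l₁)² + (u₂−p₂)² − 2r(p₁−l₁)(u₂−p₂)]
   - upper = d + √[(u₁−p₁)² + (p₂−l₂)² − 2r(u₁−p₁)(p₂−l₂)]
4. Set r = 0 when either SE is zero, since r is then undefined. This occurs in about 6% of simulated trials at 0.96 vs 0.90 and about 11% at 0.96 vs 0.96.
5. Keep the normal-theory intervals as a sensitivity analysis.

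The cost is a change of wording and a few lines of code, with no extra patients or readers. Average width rises from about 9 to 13 points at 96% and from about 16 to 17 at 90%. Intervals will be wider than necessary if the true within-patient correlation is low.
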